#### 4.1.12 Subject Withdrawal

In the absence of treatment delays due to adverse events, treatment may continue until one of the following criteria applies:

- 1. Clinically significant progressive disease, or
- 2. Intercurrent illness that prevents further administration of treatment, or
- 3. Subject request, or
- 4. General or specific changes in the subject's condition render the subject unacceptable for further treatment in the judgment of the investigator, or
- 5. Unacceptable toxicity that in the opinion of the investigator makes it unsafe to continue therapy.

It is planned that up to a total of 12 cycles of therapy will be administered for subjects deriving benefit from this regimen. Continuation of therapy for subjects completing 12 cycles of therapy may be considered on a case-by-case basis after discussion with the Principal Investigator.

#### 4.1.13 Subject Evaluability and Replacement

In the escalation phase, subjects who are not considered fully evaluable per protocol for the primary objective of safety and tolerability per Section 4.3 will be replaced. Subjects who have taken 75% or more of the planned IACS-010759 treatment in cycle 1 will be considered evaluable for MTD. Subjects who have taken less than 75% of planned medication in cycle 1, but who came off study due to a DLT will also be considered evaluable.

#### 4.1.14 Safety Monitoring and Study Stopping Rules

Safety monitoring, including analysis of PK, will be performed by a Safety Monitoring Committee, consisting of the Principal Investigator (and co-investigators as needed) and sponsor representatives (e.g., a designee from the IND Office) and the study-specific Medical Monitor. Additional investigators and staff shall participate in reviews as indicated.

An Independent Data Monitoring Board will not be utilized for this open label study.

#### 4.1.14.1 *Study Stopping Rules*

The Safety Monitoring Committee has the right to recommend to terminate or alter the study design of this clinical study at any time. The principal investigator will be involved in any decisions regarding terminating the study, temporarily suspending enrollment, or stopping ongoing treatment with study treatment. MD Anderson/IND Office (as the sponsor) has the right to terminate the clinical study at any time.

Reasons for terminating the clinical study or a study site's participation include, but are not limited to, the following:

- The incidence or severity of an adverse reaction related to treatment in this study or other studies indicates a potential health hazard to subjects
- Data recording is significantly inaccurate or incomplete
- Study site personnel are noncompliant with study procedures

#### 4.1.14.2 Protocol Violations and Deviations

Protocol violations are defined as significant departures from protocol-required processes or procedures that affect subject safety or benefit potential, or confound assessments of safety or clinical activity. A protocol deviation is a departure from the protocol that does not meet the above criteria. Protocol violations or deviations may be grouped into the following classes:

- Enrollment criteria
- Study activities (missed evaluations or visits) except for those allowed per protocol
- Noncompliance with dose or schedule, including dose calculation, administration, interruption, reduction, or delay; or discontinuation criteria
- Investigational product handling, including storage and accountability
- Informed consent and ethical issues

Every effort will be made to adhere to the schedule of events and all protocol requirements. Variations in schedule of events and other protocol requirements that do not affect the rights and safety of the subject will not be considered as deviations. Such variations may include laboratory assessments completed outside of schedule, occasional missed required research samples such as correlative assays.

#### 4.1.15 Follow-Up at Treatment Discontinuation or Early Withdrawal

Subjects who discontinue treatment for any reason should complete end-of-treatment procedures when possible. End of treatment procedures will include a physical examination, CBC with differential and platelets and chemistry. A bone marrow aspiration may be recommended only if non-response or progressive disease cannot be unequivocally diagnosed from peripheral blood. Although treatment will be discontinued at that time, all subjects who do not die, withdraw consent for follow-up, or become lost to follow-up, will remain on study for

follow-up evaluations. Subject will be followed for possible delayed emergence of IACS-010759 related toxicity at least 30 days after the last protocol treatment. Subjects who discontinue the study will be requested to return for additional PK and/or PD blood daws, approximately every 4 days, when possible, for up to 4 weeks after the last study drug administration to further explore the PK and PD activity of IACS-010759 following discontinuation of study drug. The 30-day (+/-7 days) follow-up visit will be scheduled as a clinic visit for clinical evaluation and physical examinations. If the subject cannot make it to the site for this visit, the required follow up treatment procedures may be performed by a local physician and the records forwarded to the site. The research nurse will also contact the subject by telephone and obtain a verbal assessment of the subject's condition. The phone conversation will then be documented in the subject's charts.

#### 4.1.16 Long-Term Follow-Up

Subjects who achieve any response will be followed for overall survival and response duration for up to 12 cycles. Patients who are responding well to therapy may continue therapy beyond 12 cycles after approval from the PI and sponsor.

If the disease appears to be responding to the study drug, a member of the study staff will call the subject once every 3-6 months for up to 5 years to assess the subject's health.

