### Study Objectives & Endpoints

Primary Objectives	Safety & Tolerability
	Determine Dose Limiting Toxicities
	Establish MTD and RP2D
Secondary Objectives	IACS-010759 pharmacokinetics and food effect
	Preliminary Clinical Efficacy (overall response rates, duration of
	response, progression-free survival, overall survival)
Exploratory objectives	Pharmacodynamic and exploratory biomarkers of activity of IACS-
	010759

Clinical study data will be entered into Medidata Rave, the clinical data base, via electronic case report forms. The Statistical Analysis Plan (SAP) will include detailed and specific description of all analysis to be performed on the clinical data from this study. The SAP will be finalized prior to database lock.

All statistical analyses will be performed using Version 9.4 or later of Statistical Analysis Software (SAS®). Data summaries will use descriptive statistics (number of subjects [n], mean, standard deviation [SD], Q1, median, Q3, minimum, and maximum) for continuous variables, and frequency and percentage for categorical and ordinal variables. If there are missing values, the number missing will be presented, but without a percentage. All data collected will be included in by-subject data listings.

Unless otherwise specified, all tests will be two-tailed using a 0.05 level of significance. All confidence intervals (CIs) will be two-sided 95% confidence intervals.

All subjects who received any study drug and who had any on-treatment evaluation will be included in the Full Analysis Set (FAS).

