### 4.4 Clinical Efficacy

### 4.4.1 Subject Evaluation & Statistics

The FAS will be the basis for the evaluation of clinical efficacy.

Disease assessment will be performed at the end of Cycles 1, 3, and thereafter every 2-3 cycles at the discretion of the treating physician. While the bone marrow aspirate/biopsy will be performed as clinically indicated, testing will occur at least once every 3 cycles.

Descriptive statistics will be provided for continuous variables and frequency tables will be used to summarize categorical variables. The Overall Response Rate and the proportions of subjects who experienced CR, Cri, PR, MLFS (morphologic leukemia-free state), hematologic improvements, Recurrence of Disease (RD) and Best Response measurement along with the corresponding exact 95% confidence intervals will be displayed.

Kaplan-Meier method will be used to estimate the duration of response, progression-free survival and overall survival. These time to event variables will be summarized using the 25th percentile, Median, and 75th percentile as well as the minimum and maximum time to event, calculated by Kaplan-Meier method, and will be displayed graphically.

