### • Recurrence of Disease (RD)

Relapse after CR is defined as a reappearance of leukemic blasts in the peripheral blood or  $\geq 5\%$  blasts in the bone marrow aspirate not attributable to any other cause or reappearance or new appearance of extramedullary leukemia. Relapse after PR is similarly defined with reappearance of significant numbers of peripheral blasts and an increase in the percentage of blasts in the bone marrow aspirate to > 25% not attributable to any other cause or reappearance or new appearance of extramedullary leukemia.

Best Response measurement: Response will be measured and defined for primary endpoints as the best response achieved during the first 3 cycles of therapy, or at time off study, for those subjects discontinuing treatment before the completion of 3 cycles of therapy. Best response is defined to be the best-measured response (ORR=CR+CRp+PR+MLFS) post-treatment up to that time. Best response will also be evaluated for the full treatment period using all assessments up to and including treatment discontinuation.

**Duration of Response**: length of time from the first objective evidence of response to the first objective evidence of disease progression.

**Progression-Free Survival**: length of time (up to 5 years) from the date of first treatment to the first objective evidence of disease progression or death, whichever is earlier.

**Overall Survival**: length of time from the date of first administration of study drug to the date of death from any cause.

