- Unless otherwise noted, the entry of an AE that is designated as serious in the EDC system will automatically prompt an automated email alert for a newly entered case or for an existing case where a change in status of the AE fields has been made by the site. The email alert will be sent to relevant personnel involved with the SAE case management, including the PROMETRIKA Safety Manager. In the event that the site is unable to send the information through the EDC, the site will contact the Drug Safety Management department at PROMETRIKA by [contact]) or [contact]) and forward the SAE Form and other related documents to the PROMETRIKA Safety Manager. The site will be responsible for safety reporting to the MDACC IRB.
- Serious adverse events will be captured from the time of the first protocol-specific
  intervention (study drug administration), until 30 days after the last dose of drug, unless
  the participant withdraws consent. Serious adverse events must be followed until
  clinical recovery is complete and laboratory tests have returned to baseline, progression
  of the event has stabilized, or there has been acceptable resolution of the event.
- Additionally, all serious adverse events that occur after the 30 day time period that are related to the study treatment must be reported to the Sponsor and the PROMETRIKA Safety Manager. This may include the development of a secondary malignancy.

IACS2015-001: Protocol Amendment #11 (01-21-20)

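### Survival follow-up is specified only for responders although overall survival is estimated in the whole Full Analysis Set, and duration of response does not say how death counts

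*Combined protocol and SAP*

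**What the plan says.** Who is followed for survival:

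- Section 4.1.16: "Subjects who achieve any response will be followed for overall survival and response duration for up to 12 cycles". The next paragraph adds: "If the disease appears to be responding to the study drug, a member of the study staff will call the subject", at intervals of 3 to 6 months for up to 5 years. Both sentences concern responders, and the two time limits are not reconciled.
- Section 4.1.15, on subjects who stop treatment: "all subjects who do not die, withdraw consent for follow-up, or become lost to follow-up, will remain on study for" follow-up evaluations. What it then specifies is end-of-treatment procedures, PK/PD draws for up to 4 weeks, a 30-day visit, a telephone contact with no repeat interval, and this: "Subject will be followed for possible delayed emergence of IACS-010759 related toxicity at least 30 days after the last protocol treatment". Survival is not mentioned.
- The flowcharts in section 4.2 end 30 days after the last dose and have no survival row or column.
- Section 8.1.7, on later events: "all serious adverse events that occur after the 30 day time period that are related to the study treatment must be reported". Unrelated events after that point are not required.

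What is to be analysed:

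- Section 4.4.1: "Kaplan-Meier method will be used to estimate the duration of response, progression-free survival and overall survival". The efficacy population is the Full Analysis Set (FAS), which is every treated subject with any on-treatment evaluation.
- Section 4.4.2 defines OS as first dose to death from any cause. Progression-free survival (PFS) counts progression or death over up to 5 years. Neither is restricted to responders. Duration of response (DoR) is the "length of time from the first objective evidence of response to the first objective evidence of disease progression", with no mention of death.
- No censoring rule is given for any of the three endpoints.

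**The concern.** The data collection described does not support the analysis described. A non-responder who stops treatment and dies of leukemia three months later has no stated route into the database: the flowchart is finished, the death is not a treatment-related serious adverse event, and the survival follow-up and calls are for responders. Kaplan-Meier would then treat that subject as censored about 30 days after the last dose, as though his or her later risk matched that of those still followed. Those still followed would be increasingly responders, who can be expected to live longer. Censoring that depends on prognosis in this way pushes the OS curve up.

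DoR raises a separate issue. PFS, defined next to it, counts death. DoR does not, and how a death in response is handled is not stated. If such deaths are censored, DoR reads too long.

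At stake are descriptive secondary endpoints. They are nonetheless part of the preliminary efficacy evidence from a trial whose results, according to section 3.2, will inform decisions on later studies.

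**Working it through.** The documents give no event count, power or target for OS or DoR, so there is no figure of the plan's own to reproduce. The size has to be illustrated.

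**Inputs from the documents.** Response rate p of 10-30% and a median OS of 3.8 months (section 2.1, background figures and not results for this drug); up to 48 subjects; 30-day follow-up after last dose; 12 cycles of 21 days = 252 days = 8.28 months.

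**Assumptions not in the documents.** The 3.8 months is applied to non-responders. Responder median is 6 or 10 months, and median treatment time for non-responders is 1 or 2 months. All times are exponential, death is independent of stopping, and untraced non-responders are censored at d = 30 days = 0.986 months after last dose.

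**OS, large-sample limit.** Let S and f be the survival and density functions (R responders, N non-responders), and G(t) the probability that a non-responder is not yet censored: 1 up to d, then exp(-λT(t - d)) with λT = ln 2 / median treatment time.

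- True OS: p·SR + (1-p)·SN.
- The hazard Kaplan-Meier estimates: [p·fR + (1-p)·fN·G] / [p·SR + (1-p)·SN·G].

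Example of the true value at 6 months (p = 0.3, responder median 10): 0.3 × 2^(-6/10) + 0.7 × 2^(-6/3.8) = 0.3 × 0.660 + 0.7 × 0.335 = 43.2%.

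Three of the 12 combinations (smallest, middle, largest bias):

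| p | Responder median (months) | Treatment median (months) | Median OS, true → KM (months) | 6-month OS, true → KM |
|---|---|---|---|---|
| 0.1 | 6 | 2 | 3.96 → 4.05 | 35.1% → 36.9% |
| 0.2 | 10 | 2 | 4.48 → 4.95 | 40.0% → 44.8% |
| 0.3 | 10 | 1 | 4.90 → 6.66 | 43.2% → 52.4% |

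Over all 12, median OS is overstated by 0.09 to 1.76 months (2-36%) and 6-month OS by about 2 to 9 points. Every KM median falls before 8.28 months, so the choice between the 12-cycle and 5-year limits for responders does not change these figures.

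**Unrecorded non-responder deaths.** With λN = ln 2 / 3.8, the share later than last dose plus 30 days is exp(-λN·d) × λT/(λT + λN):

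- treatment median 1 month: 0.835 × 0.792 = 66%;
- treatment median 2 months: 0.835 × 0.655 = 55%.

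**Non-responders still at risk at 6 months, out of 48 subjects.** 48 × (1-p) × SN(6) × G(6), with SN(6) = 0.335 and G(6) = 0.031 or 0.176:

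- lowest: 48 × 0.7 × 0.335 × 0.031 = 0.3;
- highest: 48 × 0.9 × 0.335 × 0.176 = 2.5.

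With full follow-up (G = 1) the range is about 11 to 14.

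**Sensitivity.**

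- Half of the non-responders traced: bias 0.03-0.39 months and 0.5-2.9 points.
- Equal hazards in the two groups: bias 0.
- Different calibration, with the *overall* true median set at 3.8 months and non-responders treated for 1-3 cycles: the KM median is 4.3-5.7 months if responders' median is twice that of non-responders, 4.6-7.4 if three times, and 3.8 if the same.
- Simulation at n = 48 (4,000 trials per scenario, responders censored at 252 days): mean KM 6-month OS 36.8-52.6% against a true 35.0-43.2%. The standard deviation of the estimate is 9.0-14.7 points.

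**DoR.** With constant hazards and a share f of first endings that are deaths without progression, censoring those deaths multiplies the median by 1/(1 - f): 1.11, 1.25 and 2.00 for f = 0.1, 0.2 and 0.5, and 1 if there are none.

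**The case against.** The strongest reply is section 4.1.15. It keeps all subjects on study without limiting this to responders, its 30 days is a minimum, and it includes a nurse's call. Read with OS to death from any cause and PFS over up to 5 years, it suggests that follow-up of everyone was intended and merely under-specified. On that reading, censoring at 30 days is an assumption, not a rule of the protocol. This is fair, and it is why the conclusion is conditional on subjects not being traced. But 4.1.15 never names survival and gives no contact schedule after the 30-day visit, while 4.1.16 does name survival and assigns it to responders. A site that follows the text literally would stop tracing non-responders.

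Second, the section on study objectives and endpoints promises a detailed SAP before database lock. That SAP could supply censoring rules and settle how death counts in DoR. It could not recover vital status that was never collected.

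Third, the size rests on assumptions. The responder medians are not in the documents, and dropping the independence of death and stopping can move the bias outside the ranges shown, so they are not bounds. If late deaths happened to be recorded while survivors were not updated, the direction could reverse. The 100% figure for DoR needs half of all endings to be deaths in response, and DoR would concern only about 5 to 14 subjects (10-30% of 48). All of this stands.

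Finally, these endpoints drive no decision rule, and the bias is smaller than one trial's sampling error. That limits the weight of the point. The error is systematic, however, and cheap to avoid.

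**Conclusion.** The concern holds as a design weakness worth correcting. The protocol plans an all-subject OS estimate but specifies survival follow-up only for responders. If non-responders are not traced and die sooner than responders, median OS is overstated by roughly 0.1 to 1.8 months and 6-month OS by 2 to 9 points, and 55-66% of non-responder deaths go unrecorded, under the exponential assumptions listed. Partial tracing shrinks the bias and equal prognosis removes it.

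The direction is expected, not certain, and confidence in the size is moderate at best. The omission of death from the DoR definition is a smaller, separate gap, and it inflates DoR only if deaths in response occur and are censored. The DLT and MTD objectives are untouched.

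**What to change.** - Section 4.1.16: follow every FAS subject for vital status, by telephone or record check, until death or a stated study cut-off. Add this to the flowcharts.
- Reconcile 4.1.15 with 4.1.16, and the 12-cycle limit with the 5-year limit.
- Section 4.4.2: end DoR at relapse, progression or death from any cause, in line with PFS. Otherwise label it time to progression and treat death as a competing event.
- State the censoring rules for OS, PFS and DoR alongside these changes.
- If vital status cannot be collected for all, say that OS is incomplete beyond 30 days after last dose.

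The cost is calls or record checks for at most 48 subjects, one reworded definition and a short censoring statement. Treatment, sample size and escalation rules do not change.

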# 4.2 Study Flowcharts

Cohorts 1 and 2	Screen						Cycle 28 day							Cyc (21 d				cle 3 days)	Су	tional cles days)	End of Study or Early Termination
Study Day	-7 to -1	1*+	2*	4	8*	9*	10*	12*	14*	17	22	28	29	36	42	49	50	70	Every	21 days	30 after last Dose
Name of Cycle Day		C1 D1	C1 D2	C1 D4	C1 D8	C1 D9	C1 D10	C1 D12	C1 D14	C1 D17	C1 D22	C1D 28	C2 D1	C2 D8	C2 D14	C2 D21	C3 D1	C3 D21	CX D20	CX D21	51
+/- days allowable										1	1	1	2	2	2	2	3	3	4	4	7
Study Drug§		Х			Х	Х	Х	Χ	Χ	Χ	Х	Х	Х	Х	Х	Х	Х	Х	Х	Х	
Disease Assessment																					
Bone marrow aspirate and/or biopsy¥	Х											Х						х	Every 2-3 cycle		х
Overall Response Rate ‡												Х						Х	,	X ‡	Х
Study Procedures & Examinations																					
Eligibility Assessment & Informed Consent	Х																				
Demographics A	Х																				
Medical history B	Х																				
MUGA/ECHO	Х																				
12-lead ECG (QTcF)	Х	X 			Х				X 		Х	X 									
Phys. Exam (inc. weight)	Х	Х			Х		Х		Х	Χ	Х	Х	Х			Х	Х	Х		Х	Х
ECOG	Х	Х											Х				Х			Х	Х
Vital Signs (Temp., HR, BP, RR)	Х	X 	X 	X 	X 	X 	X 	X 	X 	X 	X 	X 	X 	X 	X 	X 	X 	X 		Х	Х
Concomitant Medication C	Х	Х	Х	Χ	Х	Х	Х	Χ	Χ	Χ	Х	Х	Х	Х	Х	Х	Х	Х		Х	Х
Adverse Events D		Х	Х	Х	Х	Х	Х	Χ	Χ	Χ	Х	Х	Х	Х	Х	Х	Х	Х		Х	Х
Labs																					
Pregnancy test	Х																				
Blood Hematology E, I, J	Х	X 			X 	X 	X 	X 	X 	Χ	Х	Х	Х			Х	Х	Х		Х	Х
Chemistry F, I	Х	X 			X 	X 	X 	X 	X 	Χ	Х	Х	Х	X 	X 	Х	Х	Х		Х	Х
Coagulation, lipase, amylase & urinalysis G, I	Х	X 			X 	X 	X 	X 	X 	Х	Χ	Х	Х	X 	X 	Х				Х	Х
Lactate and blood pH I, K	Х	X 	X 	X 	X 	X 	X 	X 	X 	X 	X 	X 	X 	X 		Х	Х				
Research Labs																					
Blood collection- pharmacodynamics H	Х	X 			X 		X 		X 		X 	X 									Χ L
Research Bone marrow aspirate/or biopsy	Х											Х									

Notes and abbreviations provided on following page.

- + Subjects enrolled in the Food Effect group will consume a high fat meal within 30 minutes prior to study drug administration on Day 1 blood sample collection.
- § Study drug will be administered without food, at least 1 hour before and at least 2 hours after eating, with the exception of Day 1 of Cycle 1 for subjects enrolled in the Food Effect group.
- ¥ Bone marrow aspirate/biopsy will be performed as clinically indicated, at least once every 3 cycles.
- ‡ Overall Response Rate (ORR) assessment will be performed on the same schedule as bone marrow aspirate/biopsy (every 2-3 cycles during additional cycles). ORR definitions are provided in Section 5.2.2.

<sup>A including Date of Birth; sex; height; race; ethnicity

<sup>B including oncology history, radiation history

<sup>c name, indication, dose, route, start and end dates

<sup>D starting or worsening after study drug administration (signs and symptoms occurring prior to the first dose of study medication on Day 1 should be recorded under the subject's Medical History).

<sup>E complete blood count, differential, platelets

<sup>F glucose, total protein, albumin, electrolytes [sodium, potassium, chloride, total CO₂], calcium, phosphorus, magnesium, uric acid, bilirubin (total, direct), SGPT (ALT) or SGOT (AST), alkaline phosphatase, creatinine, blood urea nitrogen, CPK

<sup>G PT, PTT, fibrinogen, INR

<sup>HOxygen consumption, metabolites, protein, mRNA analysis

<sup>1 To be performed weekly during the first cycle of the increased dose for any intra-subject dose escalation

<sup>1 For purposes of data collection, test results below the limit of quantitation will be reported as "0"

<sup>k If the Investigator determines that the dose of study drug should be interrupted, additional PK, lactate and blood pH assessments will be collected pre-dose (within 2 hours of dosing) and 6 hours +/- 30 minutes post study drug administration upon resumption of dosing. If the dose of study drug is reduced, additional PK assessments will be collected pre-dose (within 2 hours of dosing) and 2, 4, 6, 8, 12 (+/- 15 mins) and 72 hours (+/- 4 hours) after starting the reduced study drug dose.

<sup>L Additional PK and/or PD draws from peripheral blood may be obtained ~every 4 days, when possible, for up to 4 weeks after last study drug administration in subjects who discontinue the study.

<sup>M In addition to the time points indicated in the Table, additional draws from peripheral blood for PK analysis may be obtained during Cycle 2 and beyond at the discretion of the Investigator.

<sup>1 collected pre-dose (within 2 hours of dosing) and 6 hours +/- 30 minutes post study drug administration

<sup>2 collected pre-dose (within 2 hours of dosing) and 2, 4, 6, 8 and 12 hours (+/- 15 mins) post study drug administration

<sup>3 collected pre-dose (within 2 hours of dosing)

<sup>4 collected 24 hours +/- 2 hours post study drug administration

<sup>5 collected 72 hours +/- 4 hours post study drug administration

<sup>6 collected pre-dose

\* Treatment will be administered as an inpatient for 24 hours on Day 1 of Cycle 1 and then starting again on Day 8 for the next 7 days.

